14.7 Missing Dates Information for Adverse Events	
14.8 Missing Date Information for Adverse Events	
14.9 Missing Date Information for Prior or Concomitant Medications	
14.9.1 Incomplete Start Date	
14.9.2 Incomplete Stop Date	
17. REFERENCES	

1. LIST OF ABBREVIATIONS

AE	adverse event
AIMS	abnormal involuntary movement scale
ALT	alanine aminotransferase
ALP	alkaline phosphatase
AST	aspartate aminotransferase
ATC	anatomical therapeutic chemical
ANCOVA	analysis of covariance
BARS	Barnes akathisia rating scale
bITT	bipolar intent-to-treat
BMI	body mass index
BP	blood pressure
BPM	beats per minute
CGI-S	clinical global impression scale-severity
CI	confidence interval
C-SSRS	Columbia-suicide severity rating scale
DBTP	double-blind treatment period
ECG	electrocardiogram, electrocardiographic
ET	early termination
eCRF	electronic case report form
GCP	Good Clinical Practice
ICE	intercurrent event
HIV	human immunodeficiency virus
ICF	informed consent form
ICH	international council on harmonization
ITT	intent-to-treat
LLN	lower limit of normal
LOE	lack of efficacy
MADRS	Montgomery-Åsberg Depression Rating Scale
MAR	missing at random
MDD	major depressive disorder
MDE	major depressive episode
MedDRA	Medical Dictionary for Regulatory Activities
mITT	modified intent-to-treat
MMRM	mixed model with repeated measure

MNAR	missing not at random
msec	millisecond(s)
PCS	potentially clinically significant
PMM	pattern mixture model
PT	preferred term
QTc	QT interval corrected for heart rate
QTcB	QT interval corrected for heart rate using the Bazett formula
QTcF	QT interval corrected for heart rate using the Fridericia formula
SAE	serious adverse event
SAP	statistical analysis plan
SAS	Simpson angus scale
SD	standard deviation
SFUP	safety follow-up period
SOC	system organ class
TEAE	treatment-emergent adverse event
TSH	Thyroid-stimulating hormone
ULN	upper limit of normal
WHO	World Health Organization
YMRS	Young Mania Rating Scale

2. INTRODUCTION

This statistical analysis plan (SAP) provides a technical and detailed elaboration of the statistical analyses of the efficacy and safety data as outlined and specified in the Protocol Amendment 4.0 of Study ITI-007-403 (dated 27 Jan 2023). Specifications of tables, figures, and data listings are contained in a separate document.

This study was originally designed as a Phase 3, randomized, double-blind, placebo-controlled, multicenter study to evaluate the efficacy and safety of lumateperone as monotherapy in the treatment of patients with Major Depressive Episodes (MDEs) associated with bipolar I or bipolar II disorder. After the study started, Study ITI-007-402 (a Phase 3, randomized, double-blind, placebo-controlled, multicenter study to evaluate the efficacy and safety of lumateperone adjunctive to lithium or valproate in the treatment of patients with MDEs associated with bipolar I or bipolar II disorder) reported its results and demonstrated lumateperone successfully reduced MDEs associated symptoms based on treatment difference in change from baseline to Day 43 in MADRS total score for lumateperone vs placebo. As a result, there was no need for an additional pivotal study for the treatment of patients with MDEs associated with bipolar II disorder.

Therefore, Study ITI-007-403 was repositioned for the treatment of patients with MDEs associated with bipolar disorder with mixed features or major depressive disorder (MDD) with mixed features. This change was described in Protocol Amendment 2.0 (dated 02 Nov 2020). A total of 100 patients had been randomized under the original protocol before the implementation of Protocol Amendment 2.0. Protocol Amendment 2.0 plans for an additional enrollment of 350 patients with approximately equal number of patients for bipolar disorder with mixed features and for MDD with mixed features.

For data analysis, the main difference between the original protocol before Protocol Amendment 2.0 and after Protocol Amendment 2.0 is in the patient populations: Original Protocol before Protocol Amendment 2.0 enrolled patients with MDE associated with bipolar I or bipolar II disorder; while after Protocol Amendment 2.0, the study enrolled patients with MDEs associated with bipolar disorder with mixed features or MDD with mixed features.

Both the Original Protocol and Protocol Amendment 2.0 consist of the same study design of a Screening Period, Double-blind Treatment Period (DBTP), and a Safety Follow-up Period (SFUP) with the same planned assessments.

Screening Period (2 Weeks)

Potential patients will be evaluated during a Screening Period lasting up to 2 weeks unless an extension of the Screening Period is approved by the Medical Monitor or Sponsor Designee.

After obtaining written informed consent, diagnostic interviews and physical examinations will be conducted, vital signs and electrocardiogram (ECGs) will be assessed, and blood samples will be collected for laboratory assessments. Patients considered potentially eligible for participation will be required to discontinue their current antidepressant treatment and/or other psychotropic drugs.

At Baseline (Visit 2), patients who continue to meet all eligibility criteria will be randomized to 1 of the 2 treatment arms (lumateperone 42 mg or matching placebo) for a 6-week DBTP.

Double-blind Treatment Period (6 Weeks)

Patients will take their first dose of study drug on the evening of Baseline (Visit 2, Day 1). A single dose will be taken each day in the evening, with or without food, for the duration of the 6-week DBTP.

Following randomization, patients will attend outpatient study visits on Days 8, 15, 22, 29, 36, and 43.

[figure not shown]
With approval from the Sponsor or Sponsor's representative, sites will be permitted to conduct remote visits if the patient is unable to travel to the site for an in-person visit or if the site is unable to schedule an in-person visit. However, all Screening and Baseline (Visit 2) assessments must be performed in person.

[figure not shown]
A patient will be defined as a treatment completer if the patient completed the double-blind treatment period (all scheduled visits up to and including Visit 8).

[figure not shown]
Safety Follow-up Period (2 Weeks)

All patients should return to the clinic for the Safety Follow-up Visit approximately 2 weeks after Visit 8/ET.

The Schedule of Evaluations for this Study is in Table 2-1.

3. STUDY OBJECTIVES

3.1 Primary Efficacy Objective

Following Protocol Amendment 2.0, the primary objective of this study is to confirm the efficacy of lumateperone 42 mg administered orally once daily compared with that of placebo as measured by mean change from baseline to Day 43 in the Montgomery-Åsberg Depression Rating Scale (MADRS) total score in patients with MDEs associated with bipolar depression with mixed features or MDD with mixed features.

Based on the primary efficacy objective, this study will evaluate the efficacy of lumateperone 42 mg based on the following three sets of patients:

[figure not shown]
- 1. All patients randomized after Protocol Amendment 2.0, which includes all patients associated with bipolar depression with mixed features and all patients associated with MDD with mixed features;
- 2. All patients with bipolar disorder (I or II) with mixed features randomized after Protocol Amendment 2.0;
- 3. All patients with MDD with mixed features.

3.2 Secondary Efficacy Objectives

3.2.1 Key Secondary Efficacy Objective

Following Protocol Amendment 2.0, the key secondary efficacy objective of this study is to confirm the efficacy of lumateperone 42 mg administered orally once daily compared with that of placebo as measured by mean change from baseline to Day 43 in the Clinical Global Impression Scale-Severity (CGI-S) score in patients with MDEs associated with bipolar depression with mixed features or associated with MDD with mixed features.

The key secondary efficacy objective will be assessed using the same three sets of patients defined for the primary efficacy objective.

4. ANALYSIS SETS

4.1 All Enrolled Set

All Enrolled Set will contain all patients who signed the informed consent form (ICF) for the study.

4.2 All Patients Randomized Set

All Patients Randomized Set will contain all patients who signed the informed consent and were randomized to study drug.

4.3 Safety Analysis Set

Safety Analysis Set will contain all patients who received at least 1 dose of study drug.

4.4 Intent-to-Treat Analysis Set

Intent-to-treat (ITT) Analysis Set will contain all randomized patients who received at least 1 dose of study drug and who had a non-missing (pre-dose) baseline assessment and at least 1 non-missing post-baseline assessment of MADRS total score.

5. PATIENTS DISPOSITION

The number of patients in the All Patients Randomized Set, Safety Analysis Set, mITT Analysis Set, bITT Analysis Set and ITT Analysis Set will be summarized by treatment group and study site. patients in the All Enrolled Set will only be summarized overall by study site.

Screen failures (ie, patients who are screened but not randomized) and the associated reasons for failure to be randomized will be tabulated overall for all screened patients. The number and percentage of patients who complete the DBTP, patients who prematurely discontinue from the DBTP and patients who enter the SFUP, patients who complete the SFUP, patients who discontinue from the SFUP will be presented by treatment group for the Safety Analysis Set as outlined in Table 2-2. The reasons for premature discontinuation during the DBTP and SFUP as recorded on the disposition pages of the electronic case report forms (eCRFs) will be summarized (number and percentage) by treatment group for the Safety Analysis Set as outlined in Table 2-2.

Page 14 of 44

7. DEMOGRAPHIC AND OTHER BASELINE CHARACTERISTICS

Demographic parameters (eg, age, sex, race, ethnicity, weight, body mass index calculated as weight $[kg]/(height [m])^2$) and other baseline characteristics will be summarized by treatment group and by overall for the Safety, and ITT Analysis Sets.

Demographic and baseline characteristics will also be summarized separately for patients randomized before Protocol Amendment 2.0 in the Safety and ITT Analysis Sets, for patients randomized after Protocol Amendment 2.0 in the Safety and mITT Analysis Sets, for two subpopulations of bipolar disorder with mixed features and MDD with mixed features in the mITT Analysis Set, and for patients in the bITT Analysis Set.

Medical and surgical history/physical findings will be summarized by treatment group, system organ class (SOC), and preferred term (PT) separately for patients randomized before Protocol Amendment 2.0, and for patients randomized after Protocol Amendment 2.0 separately for the Safety Analysis Set. Bipolar and psychiatric diagnosis and history will be summarized by treatment group and by overall for the Safety Analysis Set and will include current diagnosis, whether the current major depressive episode has psychotic features or whether patient meets criteria for anxious distress, age of patient at first diagnosis of bipolar disorder or MDD, number of lifetime depressive and manic/hypomanic/mixed episodes, number of depressive and manic/hypomanic/mixed episodes within the past year, whether and how many times patient has been hospitalized for any psychiatric related issues.

Baseline efficacy parameters will be summarized by treatment group for patients randomized before Protocol Amendment 2.0 in the ITT Analysis Set, for patients in the mITT Analysis Set and for patients in the bITT Analysis Set. Baseline efficacy parameters will also be summarized by treatment group for patients randomized after Protocol Amendment 2.0, and for two subpopulations of bipolar disorder with mixed features and of MDD with mixed features in the ITT Analysis Set.

Prior medication is defined as any medication which started and stopped before the date of the first dose of double-blind study drug. *Prior Concomitant medication* is defined as any medication which started before the date of the first dose of double-blind study drug and stopped or is ongoing after the date of the first dose of double-blind study drug. *Concomitant medication* is defined as any medication taken on or after the date of the first dose of double-blind study drug. *Concomitant medication* is defined as any medication taken on or after the date of the first dose of double-blind study drug. The *World Health Organization (WHO) Drug Dictionary*, version MAR21 or newer, will be used to code medications.

Prior medication, prior concomitant medication, and concomitant medication will be summarized by treatment group and Anatomical Therapeutic Chemical (ATC) code and preferred term for the Safety Analysis Set as outlined in Table 2-2. Each patient will be counted only once for each ATC code and preferred term.

Any concomitant medication started after the date of the last dose of double-blind study drug will not be included in the summary but will be included in the patient data listings.

Prior medication, prior concomitant medication, concomitant medication, and prior concomitant or concomitant use of Zolpidem and other protocol permitted rescue medication during the study will be summarized by treatment group for patients randomized before Protocol Amendment 2.0, for patients randomized after Protocol Amendment 2.0 and for two subpopulations of bipolar disorder with mixed features and of MDD with mixed features in the Safety Analysis Set.

8. EXTENT OF EXPOSURE AND TREATMENT COMPLIANCE

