2.2 Rationale

The screening phase permits evaluation of diagnosis of Bipolar I or Bipolar II Disorder with mixed features or MDD with mixed features. Laboratory and ECG assessments enable confirmation of eligibility for inclusion into the study. Unless an extension of screening is approved by the Medical Monitor or Sponsor designee, the screening phase will be no longer than 2 weeks (14 days).

At Baseline (Visit 2), patients will be randomly assigned in a 1:1 ratio to 1 of 2 treatment groups (lumateperone 42 mg or placebo) and will receive treatment for up to 6 weeks. In order to ensure patient safety, a mandatory follow-up visit will be performed approximately 2 weeks after Visit 8/ Early Termination (ET). Any ongoing AEs at the follow-up visit must be followed until resolution, until the AE stabilizes, until it is determined to be non-clinically significant, or until the patient is lost to follow-up.

Lumateperone 42 mg was selected to evaluate the efficacy seen with this dose in bipolar depression studies ITI-007-404 and ITI-007-402. This dose delivers full occupancy of the cortical 5-HT_{2A} receptors (>85% occupancy) with modest striatal D₂ receptor occupancy and SERT occupancy. Data from human PET brain receptor occupancy studies with lumateperone indicate that a dose as low as 10 mg is associated with >85% occupancy of cortical 5-HT_{2A} receptors, while the 42-mg dose demonstrates approximately 40% striatal D₂ receptor occupancy. SERT occupancy has been demonstrated to be comparable to D₂ receptor occupancy. Moreover, in patients with schizophrenia and

bipolar depression, once-daily oral administration of lumateperone 42 mg has been well tolerated with no dose titration needed and with a safety profile similar to placebo with up to 6 weeks' treatment duration. There is evidence that MDD patients with mixed features respond to similar doses of D2 receptor antagonists as bipolar depression patients with mixed features (Suppes et al, 2016; Swann et al, 2017). Therefore, a fixed-dose design will be employed in this study with once daily oral administration of lumateperone 42 mg (or placebo).

A placebo control group is needed to establish the efficacy of a new compound.

The treatment period duration of 6 weeks was chosen because it is considered an acceptable period to demonstrate efficacy in this patient population.

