8.3.1.4 Time Period and Frequency of AE Assessment and Follow-up

The Investigator will report all AEs and SAEs from the time informed consent was obtained until 30 days after the final protocol-defined study visit or the last known dose of study drug (if the final visit does not occur).

All AEs must be followed to satisfactory resolution, until the Investigator deems the event to be chronic or not clinically significant, or until the patient is considered to be clinically stable.

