9.4.2 Prior and Concomitant Medications

Prior, concomitant, and post-treatment medications, defined by start and stop dates relative to study drug administration, will be summarized by Anatomical Therapeutic Chemical (ATC) code, preferred term and treatment group for the Safety Analysis Set as outlined in Table 9-1. Patients with multiple occurrences of a medication in the same preferred term will only be counted once within the preferred term.

During the study, a patient may be treated with zolpidem as described in Section 6.6. The number and percent of patients in the Safety Analysis Set receiving zolpidem and the total number of days on zolpidem will be summarized by treatment group for the Screening Period, for each week during the Double-blind Treatment Period and for post-treatment with lumateperone.

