10.1 Adverse Events

[figure not shown]
AEs will be coded using the Medical Dictionary for Regulatory Activities, version 20.1 or newer.

Treatment emergent AEs (TEAE) are defined as any AEs, regardless of the relationship to study drug, that occur or worsen in severity after the first dose of study drug and on or before the date of last dose of study drug plus one day. An event that occurs is referring to an event that did not occur before, or it started 2 days or more after the end date of the previous event for the same preferred term. Severity increases is referring to an increase in severity for a continuous event during the DBTP.

The number and percentage of patients reporting TEAEs in each treatment group will be tabulated by SOC and PT; by SOC, PT, and severity; and by SOC, PT, and relationship to study drug. If more than 1 AE is coded to the same PT for the same patient, the patient will be counted only once for that PT using the most severe and most related occurrence for the summarization by severity and by relationship to study drug, respectively.

The incidence of common (\geq 5% of patients in any treatment group) TEAEs will be summarized by PT and treatment group and sorted by decreasing frequency for the lumateperone 42 mg group.

The incidence of serious adverse events (SAEs) and of AEs leading to premature discontinuation of study drug will also be summarized by SOC, PT, and treatment group and will be sorted by decreasing frequency for lumateperone 42 mg group. Listings will be presented for patients with SAEs, patients with AEs leading to premature discontinuation of study drug, patients who died (if any) and patients who died (if any) with AEs.

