14.9.2 Incomplete Stop Date

The following rules will be applied to impute the missing numeric fields for an incomplete prior or concomitant medication stop date. If the imputed stop date is before the start date (imputed or non-imputed start date), the imputed stop date will be equal to the start date.

Missing month and day

- If the year of the incomplete stop date is the same as the year of the last dose of doubleblind study drug, the month and day of the last dose of double-blind study drug will be assigned to the missing fields
- If the year of the incomplete stop date is before the year of the last dose of double-blind study drug, *December 31* will be assigned to the missing fields
- If the year of the incomplete stop date is after the year of the last dose of double-blind study drug, *January 1* will be assigned to the missing fields

Missing month only

• If only the month is missing, the day will be treated as missing and both the month and the day will be replaced according to the above procedure

Missing day only

[figure not shown]
- If the month and year of the incomplete stop date are the same as the month and year of the last dose of double-blind study drug, the day of the last dose of double-blind study drug will be assigned to the missing day
- If either the year of the incomplete stop date is before the year of the date of the last dose of double-blind study drug or if both years are the same but the month of the incomplete stop date is before the month of the date of the last dose of double-blind study drug, the last day of the month will be assigned to the missing day

• If either the year of the incomplete stop date is after the year of the date of the last dose of double-blind study drug or if both years are the same but the month of the incomplete stop date is after the month of the date of the last dose of double-blind study drug, the first day of the month will be assigned to the missing day.

15. CHANGES TO ANALYSES SPECIFIED IN THE PROTOCOL

There are no changes to the analyses specified in the protocol.

	-	

17. REFERENCES

Lu K. Sample size calculations with multiplicity adjustment for longitudinal clinical trials with missing data. Statist Med. 2012; 31:19-28.

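### The SAP drops the by-arm post-treatment medication and zolpidem summaries of Protocol 9.4.2 while declaring no changes, and shows no by-arm table for non-serious AEs that start after last dose plus one day

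*SAP*

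**What the plan says.** **Medications.** Protocol 9.4.2 states: "Prior, concomitant, and post-treatment medications, defined by start and stop dates relative to study drug administration, will be summarized". The breakdown is by ATC code, preferred term and treatment group. The same section adds a by-arm zolpidem summary for screening, for each treatment week and for the time after treatment.

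SAP Section 7 defines three classes only: prior, prior concomitant and concomitant. It then says: "Any concomitant medication started after the date of the last dose of double-blind study drug will not be included in the summary". Such medications are kept in the data listings. For zolpidem it plans a summary of prior concomitant or concomitant use. SAP 15 reads: "There are no changes to the analyses specified in the protocol".

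**Adverse events.** Protocol 2.2 gives the reason for the follow-up visit: "In order to ensure patient safety, a mandatory follow-up visit will be performed approximately 2 weeks after" Visit 8 or early termination. Protocol 8.3.1.4 has AEs reported "until 30 days after the final protocol-defined study visit or the last known dose of study drug", the second limb applying when the final visit does not take place. A TEAE is an event that starts or worsens after the first dose and "on or before the date of last dose of study drug plus one day" (SAP 10.1; Protocol 9.4.6 has the same rule). The tables by SOC and PT, by severity, by relationship and for common events are all TEAE tables.

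**The concern.** The trial makes an off-drug safety visit mandatory and keeps collecting AEs and medications around it. The visible SAP then gives no by-arm summary of medications started after the last dose, and none of the non-serious AEs that start then.

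The first omission contradicts a protocol commitment, and the SAP section meant to record such departures says there are none. A reader relying on SAP 15 would expect every analysis in the protocol to be produced.

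What is at stake is descriptive. The safety objective (Protocol 3.3) is a comparison with placebo. Protocol 6.6 requires patients to come off antidepressants and other psychotropics for the study, so new treatment after the last dose is foreseeable. Non-serious events such as insomnia or agitation after stopping are possible too. The documents give no expected rate for either. Without by-arm counts, a difference between arms would have to be pieced together from listings.

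**Working it through.** The plan states no figure on this point, so the check is a comparison of texts and a count of days.

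**1. Medications**

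| Item | Protocol 9.4.2 | SAP Section 7 |
|---|---|---|
| Started before the last dose and continued | summarised by arm | summarised by arm |
| Started after the last dose | summarised by arm as post-treatment | listing only |
| Zolpidem after treatment | summarised by arm | only prior concomitant or concomitant use planned |

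The second row is a direct contradiction and the third an omission. Protocol Section 9 lets the SAP change analysis methods without an amendment, but says that such changes will be documented in the SAP. SAP 15 documents none.

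**2. AE windows for a completer**

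Inputs: follow-up visit on Day 57 (SAP Table 14-1); reporting ends 30 days after the final visit (Protocol 8.3.1.4); TEAE window ends at last dose + 1 day. Assumption: last dose on the evening of Day 42, with Visit 8 on Day 43. Day 43 as the last dose is the alternative.

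- TEAE window end: 42 + 1 = Day 43.
- Not covered up to the follow-up visit: Days 44–57, so 57 − 43 = 14 days.
- End of AE reporting: 57 + 30 = Day 87.
- Not covered up to the end of reporting: Days 44–87, so 87 − 43 = 44 days.
- With last dose on Day 43: 57 − 44 = 13 days and 87 − 44 = 43 days.

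**3. Which visible outputs reach the follow-up period**

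- The SAE incidence table by SOC, PT and arm (SAP 10.1) carries no treatment-emergent limit, so SAEs in follow-up count as written.
- Deaths are listed (SAP 10.1).
- Entry into, completion of and discontinuation from follow-up are tabulated by arm (SAP Section 5).
- C-SSRS is tabulated by arm for the period after double-blind treatment, and AEs of patients with suicidal ideation or behavior are listed (SAP 10.5.1).
- For a non-serious AE that starts after last dose + 1 day, SAP 10.1 as shown has no by-arm table.

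Protocol 9.4.6 names reported AEs alongside TEAEs and SAEs among the data to be summarised. This gives some support for a table beyond TEAEs, but it does not specify one.

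**The case against.** **The AE rule is the same in both documents.** This stands. Neither document expressly promises an incidence table of post-treatment non-serious AEs, so the AE part is a gap in reporting and not an inconsistency.

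**Absence cannot be proved.** This stands for AEs. SAP Section 2 places table specifications in a separate document, and Table 2-2 is not in the public text. It does not rescue the medication part: a post-treatment table in those specifications would meet the protocol but contradict the SAP's own sentence.

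**Protocol Table 9-1 lists only prior and concomitant medication.** True, but a short row label does not cancel the explicit wording of 9.4.2, which also names post-treatment zolpidem.

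**The data are not lost.** Correct. Later medications are in listings, and those started earlier and continued are still summarised. Listings are not the by-arm summaries that the protocol describes.

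Three stronger readings are tempting, and the documents do not support them.

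- *Most of the safety experience goes unreported.* A share of days depends on the end point chosen: up to the last visit, 43/57 = 75% of days are covered. Days are not events, and SAEs are counted throughout.
- *Early stoppers are affected most.* Take a patient whose last dose is on Day 14, with early termination on Day 15, follow-up on Day 29 and reporting to Day 29 + 30 = Day 59. The uncovered days are 59 − 15 = 44, the same as for the completer.
- *Nothing is available to interpret the post-treatment C-SSRS results.* SAP 10.5.1 lists the AEs of these patients, and later medications are listed too.

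**Conclusion.** The medication part is established from the text alone. The SAP removes a by-arm summary of post-treatment medications, leaves out post-treatment zolpidem, and wrongly states that nothing has changed. It concerns only medications started after the last dose.

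The AE part holds in limited form. For a completer with last dose on Day 42, non-serious AEs starting in the 14 days up to the follow-up visit, or the 44 days up to the end of reporting, appear in no visible by-arm table. This rests on the assumed last-dose day (13 and 43 days if it is Day 43) and on the unseen specifications containing no such table. How many events are involved cannot be judged from the documents.

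A reader might infer that the trial was meant to measure withdrawal effects and fails to. No such objective is visible: Protocol 2.2 gives patient safety as the reason for the visit. No efficacy result, power figure or TEAE count is affected.

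**What to change.** 1. Restore in SAP Section 7 the by-arm summary of post-treatment medications and the post-treatment zolpidem summary of Protocol 9.4.2. If they were dropped on purpose, say so in SAP 15 and justify it. Either way the SAP text has to change.
2. Keep the TEAE definition. Add to SAP 10.1 one descriptive table by SOC, PT and treatment group for AEs that start or worsen after last dose plus one day, up to the end of AE collection. If the separate specifications already contain it, refer to it in SAP 10.1.

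The cost is two or three descriptive tables from data already collected, with no inference and no effect on type I error. The drawback is that AEs after treatment are partly confounded by newly started therapy. The restored medication summary would make this visible, and the AE table should carry a note to that effect.
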